- Pharmacokinetics Plasma and CSF levels of K0706 and any relevant metabolites.

Safety / Tolerability Endpoints:

- Vital Signs
- Electrocardiography (ECG)
- Laboratory values
- Adverse Events (AEs)
- •

Exploratory Endpoints:

- Skin pathological findings that correlate with PD,
- Blood and CSF levels of emerging biomarkers (progression or target engagement of K0706.
- Brain DaT SPECT an imaging tool that is a marker of dopaminergic cell health.
- •

Part 2 (Weeks 40 to 80)

Protocol CLR 18 06, EudraCT 2018-003337-15 A06 – 23 October 2023 K0706 Name of Sponsor: Sun Pharma Advanced Research Company Limited (SPARC) Name of Investigational Product: K0706 / placebo **Primary endpoint:** • Incidence of treatment-emergent adverse events **Secondary endpoints:** • Change from Week 40 (Baseline for Part 2) to Week 76 of the long-term extension study in the MDS-UPDRS Part III score • Change from Week 40 (Baseline for Part 2) to Week 76 of the long-term extension study in MDS-UPDRS Parts II and III sum score • Change from Week 40 (Baseline for part 2) through Week 76 in MDS-UPDRS Part IA, Part IB, Part I total, Part II total, and Part III sub-scores Change in MDS-UPDRS grand total score (sum of Parts I, II, and III) from Week 40 (Baseline for part 2) through Week 76 Time from Week 40 (Baseline for Part 2) to initiation of symptomatic PD medications in the longterm extension study **Exploratory endpoints:** Change in the mean MDS- UPDRS Parts I, II and III scores between the early-start and delayedstart groups at 76 weeks

- Evaluation of slopes of the mean MDS-UPDRS Parts II and III scores over time in part 2 for the early-start group as compared to the delayed-start group
- The proportion of patients starting symptomatic PD treatment

Study Design
This is a randomized, double-blind, placebo-controlled, to evaluate the efficacy, safety and tolerability of two doses of K0706 compared to placebo in subjects with early PD. This study consists of two parts. Part 1 is designed to evaluate the
efficacy, safety, and tolerability of two dose levels of K0706 compared to placebo in subjects with early
PD who are not receiving dopaminergic therapy. Part 2 is an optional long-term extension study to assess the long-term safety/tolerability of K0706 in subjects with early PD.
Part 1:

Name of Sponsor: Sun Pharma Advanced Research Company Limited (SPARC)
Name of Investigational Product: K0706 / placebo

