5.0 STUDY DESIGN

5.1 Description of Type and Design of Study

This is a randomized, multicenter, double-blind, placebo-controlled, study to evaluate the efficacy, safety, and tolerability of two dose levels of K0706 in subjects with early PD who are not receiving symptomatic therapy. This study consists of two parts. Part 1 is designed to evaluate the efficacy, safety, and tolerability of two dose levels of K0706 compared to placebo in subjects with early stage PD. Part 2 is an optional long-term extension study assess the long-term safety/tolerability of K0706 in subjects with early PD. Part 1 Subjects will visit the clinic for the part 1 Screening Visit, be screened based on the eligibility criteria, and provide written informed consent. Confirmation of eligibility at the Part 1 Baseline visit will require the availability of laboratory results, as well as Investigator interpretation of Magnetic Resonance Imaging (MRI) of the brain and central reading of a DaT SPECT scan (obtained prior to or as part of this study). . The screening period is summarized in the Screening Period Flow Diagram (Figure 17-1). Following confirmation of eligibility at the Part 1 Baseline visit, all subjects will be randomized, have baseline assessments performed, and receive the first dose of the study drug. This will be followed by planned visits as per the Schedule of Assessments. The part 1 treatment assessment for efficacy will be performed at Week 40. Subjects choosing not to continue in part 2 will return for a follow-up visit at Week 44. Subjects will provide blood for the measurement of standard safety laboratory parameters and of levels of K0706.

If a subject chooses to begin taking symptomatic PD medication during the trial, they will be discontinued from the study and will be asked to come in for an Early Discontinuation (ED) visit for their final assessment. They will be requested to perform this visit prior to initiation of symptomatic medication. The date of initiation of symptomatic medication will be documented appropriately in source notes and eCRF.

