8.4 Eliciting, Documentation and Reporting of Adverse Events

Information on AEs will be derived by questioning the subjects in general terms (e.g., "How do you feel?" or "How have you been feeling since the last questioning?" respectively), by subjects' spontaneous reports, or by observation.

AEs will be documented on the source document. Trained monitors will check the entries on the source document. The AE will be transcribed to the AE eCRF-sections. The following information will be given for each AE: Description of the AE, start date, stop date, severity, pattern, action taken, outcome, seriousness, dose of study drug, and relationship to the study medications. The dose of the study drug assigned to an AE will be the dose the subject was assigned to take on the date the subject reported the AE first began.

The AE / SAE collection period for safety surveillance begins when the subject signs the Informed Consent Form and continues until the follow-up visit, or if the follow-up visit does not occur within the defined time window, then 30 days post the end of treatment visit or 30 days post the last dose of study drug for subjects with early discontinuation.

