9.8.1 Adverse Event Analysis

An AE is considered treatment-emergent if it was not present prior to the first dose of treatment or, if it was present, it worsened in severity or treatment attribution. AEs will be coded using the most recent version available of Medical Dictionary for Regulatory Activities (MedDRA) and assigned severity levels as described in Section 8.5.

The number and percentage of subjects reporting TEAEs will be tabulated by severity, system organ class, causality, and preferred term, with a breakdown by treatment group. Similarly, the number and percentage of subjects reporting treatment-emergent SAEs will be tabulated, as well as TEAEs leading to discontinuation of study drugs.

[figure not shown]
Deaths, other SAEs, and other significant AEs, including those leading to discontinuation of study drugs, will be listed. AEs will also be summarized by actual dose at the time of onset of the AE to account for possible dose reductions over the course of the study.

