3.5 Safety Analysis Set

3.5.1 Safety Analysis Set, Part 1

All subjects treated with at least one dose of study medication in Part 1 of the study will be included in the Safety Analysis Set, Part 1. This population will be used for all the Safety analyses for Part 1.

3.5.2 Safety Analysis Set, Part 2

All subjects treated with at least one dose of study medication in Part 2 of the study will be included in the Safety Analysis Set, Part 2. This population will be used for all the Safety analyses for Part 2.

3.7 Pharmacokinetics Analysis Set, Part 1

The PK Analysis Set, Part 1 will include all subjects who received at least one dose of study medication in Part 1 of the study and had at least one blood sample taken at a later time to measure K0706 concentration level. This population will be used for PK-related analyses for Part 1.

3.8 All Enrolled Set, Part 2

[figure not shown]
All subjects who had a Part 2 visit, including the Part 2 baseline visit (e.g., eCRF Visit 13), will be included in the All Enrolled Set, Part 2. This population will be used for the summary of disposition, demographics and baseline characteristics for Part 2.

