 - Leading to discontinuation of study treatment
 - Leading to death
- Any serious study treatment-related TEAE
 - Leading to discontinuation of study treatment
 - Leading to death
- The number and percentage of subjects reporting each TEAE and the count of number of events will be summarized by SOC and PT for the following types of TEAEs:
 - TEAEs
 - TEAEs Leading to Discontinuation of Study Treatment
 - TEAEs Leading to Death
 - TEAEs by Maximum Severity
 - TEAEs by Relationship to Treatment
 - TEAEs by Relationship and Maximum Severity
 - Study Treatment-Related TEAEs
 - Study Treatment-Related TEAEs Leading to Discontinuation of Study Treatment
 - Study Treatment-Related TEAEs Leading to Death

- Serious TEAEs
- Serious TEAEs Leading to Discontinuation of Study Treatment
- Serious TEAEs Leading to Death
- Study Treatment-Related Serious TEAEs
- Study Treatment-Related Serious TEAEs Leading to Discontinuation of Study Treatment
- Study Treatment Related Serious TEAEs Leading to Death
- The number and percentage of subjects who died will be summarized
- The number and percentage of subjects reporting each TEAE and the number of events will be summarized by PT

AEs for Part 1 of the study will be summarized by default descriptive summary statistics for categorical variables by formulation category and overall, using the Safety Analysis Set, Part 1, as follows:

- An overview of TEAEs including the number and percentage of subjects with at least one of each mentioned TEAE type above.
- The number and percentage of subjects reporting each TEAE and the number of events will be summarized by SOC and PT.
- The number and percentage of subjects reporting each TEAE and the count of number of events will be summarized by PT.

In the above summaries, subjects with more than one TEAE within a particular SOC are counted only once for that SOC. Similarly, subjects with more than one TEAE within a particular PT are counted only once for that PT.

For summaries by maximum severity, subjects with multiple TEAEs within a particular SOC or PT will be counted under the category of their most severe TEAE within that SOC or PT. TEAEs with missing severity will be included in the overall count of subjects with TEAEs, but will not be included in the counts of subjects with TEAEs within a SOC or PT.

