9.8 Extent of Exposure

Duration of exposure will be calculated in weeks as:

Duration of exposure will be summarized by treatment group and overall for Parts 1 and 2 of the study separately.

The total number and percent of doses administered per subject (and the number of subjects with doses administered since previous visit) at each scheduled site visit will be summarized using descriptive statistics by treatment group and overall.

[figure not shown]
The percentage of doses administered per subject will be calculated as the total number of doses administered divided by the total planned doses, expressed as a percentage.

Total number of doses administered per Visit will be defined as:

• For Part 1 of the study:

- For the first post-Baseline visit → (Date of the visit date of first dose for Part 1 number of doses missed since last visit)
- For subsequent visits → (Date of the visit date of the prior visit number of doses missed since last visit)
- For the last on-treatment visit \rightarrow (Date of the last dose for Part 1 date of the prior visit number of doses missed since last visit + 1)
- For Part 2 of the study:
 - For the first post-Baseline visit → (Date of the visit date of first dose for Part 2 number of doses missed since last visit)
 - For subsequent visits → (Date of the visit date of the prior visit number of doses missed since last visit)
 - For the last on-treatment visit \rightarrow (Date of the last dose for Part 2 date of the prior visit number of doses missed since last visit + 1)

Total number of doses administered in Part 1 or Part 2 will be calculated as the sum of the doses administered per Visits in Part 1 or Part 2, respectively.

A listing of overall treatment exposure data, including the first and last dates of treatment, transition dates from capsules to powder formulation, and dates of the study treatment dose reductions will be presented for Parts 1 and 2 of the study separately, using the Safety Analysis Set, Part 1 and Safety Analysis Set, Part 2, respectively.

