12.2 General rules for Statistical Reporting

In general, statistical reporting and analyses will be created separately for Part 1 and Part 2.

The default summary statistics for quantitative variables will be the number of observations (n), mean, SD, median, minimum (min) and maximum (max), for those subjects with data. In addition, geometric mean and CV% of geometric mean will be reported for PK parameters.

All summary statistics will be rounded (using the more decimal place than the raw value, except for the SD and SE values that will be presented to 2 more decimal places than the raw value, and minimum and maximum values that will be presented with the same decimal precision as the raw value. All summary statistics for PK data will be rounded (using the analysis) and presented to 3 significant figures, except for the geometric CV values that will be presented to 1 decimal place.

For qualitative variables, the number (n) and percentage (%) of subjects with non-missing data per category will be the default summary presentation, and where appropriate and present, the number of missing values as a "Missing" category. The number of subjects in the analysis population will be used as denominator for percentages calculation, unless stated otherwise in Tables, Figures and Listings (TFL) mock shell(s).

All statistical comparisons and tests will be performed at the significance level unless specifically stated otherwise.

All central laboratory test results will be provided in International System of Units (SI) and all local laboratory test results will be provided in conventional units.

For the TFL, the results will be summarized or presented in Refer to Appendix of the TLF mock shells for the SI unit corresponding to each laboratory test and the precision level in which each laboratory test is reported by the central laboratory.

Specifications for table, figures and data listing formats can be found in the TFL shells specifications for this study. Please refer to "2. General Format Guidelines" section within TFL shells for more details on presentation of results.

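### Adverse-event incidence, including the Part 2 primary endpoint, is planned only as crude percentages with no adjustment for time at risk

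*SAP*

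**What the plan says.** - **Content of the tables.** SAP 9.1 gives, for each type of TEAE, "The number and percentage of subjects reporting each TEAE and the count of number of events will be summarized by SOC and PT". Protocol 9.8.1 plans the same kind of table: "The number and percentage of subjects reporting TEAEs will be tabulated by severity, system organ class, causality, and preferred term".
- **Denominator.** SAP 12.2: "The number of subjects in the analysis population will be used as denominator for percentages calculation", unless the table shells say otherwise. The Part 2 safety set in SAP 3.5 is "All subjects treated with at least one dose of study medication in Part 2 of the study", so one dose is enough to count in full.
- **Status of the endpoint.** The Part 2 primary endpoint in the protocol synopsis is "Incidence of treatment-emergent adverse events". No time base is given, and SAP 9.0 and 9.1 apply the same tables to both parts.
- **Early exit.** Protocol 5.1 says of subjects who choose to start symptomatic PD medication that "they will be discontinued from the study and will be asked to come in for an Early Discontinuation (ED) visit".
- **End of AE collection.** Protocol 8.4 runs collection to the follow-up visit or, if that is missed, to 30 days after the end-of-treatment visit or "30 days post the last dose of study drug for subjects with early discontinuation".
- **Part 1 window.** SAP 9.1 stops Part 1 TEAEs at the first Part 2 dose for subjects who roll over. For the others it counts all TEAEs.
- **Exposure.** SAP 9.8: "Duration of exposure will be summarized by treatment group and overall", separately for the two parts. The readable text never uses it as a denominator for AEs.

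**The concern.** A crude percentage estimates the risk over a fixed period only if nearly everyone is observed for that period. Here the design removes subjects early, and one of the reasons may depend on treatment: SAP 8.2.1.3 tests whether K0706 postpones the start of symptomatic medication, which is itself an exit event. If K0706 does so, placebo subjects are observed for less time and the crude comparison tilts against the drug. If other exits unrelated to the AE being counted are more common on K0706, it tilts the other way.

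SAP 8.1.6 foresees differential dropout, but only for efficacy and only with post hoc analyses. The readable safety sections have no counterpart. What is at stake is the Part 1 comparison of each dose with placebo and, in Part 2, the absolute incidence that forms the primary endpoint.

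**Working it through.** The plan states no AE risk and no exit rate, so there is no figure of its own to reproduce. All risks and exit rates below are assumptions. From the documents come the treatment periods (40 weeks, then 36), the 1:1:1 allocation and the planned 506 subjects, about 169 per arm.

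**1. Part 1, equal true hazard, exits spread evenly over 40 weeks and independent of AEs.** With a true 40-week risk of 40%, λ = -ln(0.6)/40 = 0.01277 per week.

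Crude % = (1-d) × 0.40 + d × [1 - (1 - e^(-40λ))/(40λ)], where d is the exit proportion. The bracket is 1 - 0.40/0.5108 = 0.217.

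| Exits d | Crude % | Gap from 10% arm |
|---|---|---|
| 10% | 0.90×0.40 + 0.10×0.217 = 38.2 | – |
| 25% | 0.75×0.40 + 0.25×0.217 = 35.4 | 2.7 |
| 35% | 0.65×0.40 + 0.35×0.217 = 33.6 | 4.6 |

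Swapping the arms (25% exits on placebo, 10% on K0706) gives 2.7 points against K0706.

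**2. Counting AEs for 4 weeks after a dropout's last dose, with completers closing at Week 40.** The bracket becomes 1 - e^(-4λ) × 0.783 = 1 - 0.950 × 0.783 = 0.256. The crude values are 38.6%, 36.4% and 35.0%, so the gaps are 2.2 and 3.6 points. Completers who do not roll over get the same extra window, which limits this reduction.

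**3. The unequal Part 1 window.** A completer followed to Week 44 has risk 1 - 0.6^(44/40) = 43.0% against 40% at Week 40, or 3.0 points. Between arms this is multiplied by the difference in the share who decline Part 2: a difference of 20 percentage points would give 0.2 × 3.0 = 0.6 points.

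**4. Effect of the adjustment.** Under a constant hazard, expected first events equal λ times expected time at risk. In step 1 the mean time at risk is 0.382/0.01277 = 29.9 weeks, 0.354/0.01277 = 27.7 weeks and 0.336/0.01277 = 26.3 weeks. The rate is the same in all three: 1.28 per 100 subject-weeks, about 66 per 100 subject-years (× 52). The false gap disappears.

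**5. Constant exit hazard instead of even exits.** Crude % = L/(L+D) × (1 - e^(-(L+D)T)), with L = -ln(1-p)/T and D = -ln(1-d)/T.
- p = 30%, d = 10% versus 30%: 28.6% versus 25.5%. T cancels, so the same holds over the 36 weeks of Part 2.
- p = 30%, d = 10% versus 15%: 28.6% versus 27.8%, under one point.
- A truly worse arm (33% versus 30%) with exits of 30% versus 10%: 28.1% versus 28.6%. The order reverses.

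**6. Two cases that limit the point.**
- All AEs begin within 4 weeks: with p = 30% and d = 10% versus 30%, crude is 29.9% versus 29.5%.
- Exits caused by the AE: true risks 30% versus 40%, half of the second arm's AEs leading to exit and 10% independent exits in each arm. Crude is 28.6% versus 38.1%, so the arm with more exits correctly looks worse.

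**The case against.** Four arguments have weight.

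- **No document says that exits differ by arm.** SAP 8.1.6 is conditional, and Protocol 2.3.1 expects most early-stage subjects to manage 40 weeks without dopamine replacement. A reader might infer that unequal exit is a fact of this trial. It is only a possibility that the design creates.
- **An AE that causes exit is already counted**, under any TEAE and under TEAEs leading to discontinuation. A reader might infer that more AE dropout on K0706 would hide its harm. For the AE that causes the exit, the second case in step 6 shows otherwise; only later, unrelated AEs are lost. For the same reason, larger gaps obtained by placing all K0706 exits in the first weeks are not supported: the natural cause of such early exits is AEs, and the formula assumes exits independent of them.
- **The plan gives more than percentages.** Event counts, exposure by arm and discontinuations by arm are all tabulated, so a reader could form a rough overall event rate. That is not a first-event rate by preferred term, and the plan does not compute one.
- **Part 2 has no placebo arm.** A reader might carry the Part 1 comparison over to the Part 2 primary endpoint. There the issue is understated absolute incidence and the comparison of three active groups.

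Some text cannot be seen. The SAP 9.1 sentence on statistical comparison of AEs has lost its opening, and SAP 12.2 lets the table shells change the denominator. A hidden adjustment cannot be fully excluded, although SAP 9.1 reads as nearly complete.

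Planned treatment duration is the same in all arms, so the crude tables are a coherent description and no error in themselves. What remains is that they are the only planned measure of incidence.

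**Conclusion.** The point holds as a gap, in conditional form. In the readable text AE incidence is planned only as subject percentages with event counts, with no allowance for time at risk, in a design that can make that time unequal. The bias needs three things together: exit times that differ by arm, AEs that accrue through follow-up, and exits unrelated to the AE counted.

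On the assumptions of steps 1 and 2 it is about 2-5 points at a 40% risk, and under one point in the example with exits of 10% versus 15%. For scale, the standard error of one dose-placebo difference at 40% risk is √(2 × 0.4 × 0.6/169) = 5.3 points. The distortion is therefore modest for any single comparison, but it is systematic, can reverse a small true difference, and is cheap to prevent. The documents do not support a claim that the high-exit arm will look safer.

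**What to change.** In SAP 9.1, keep the crude tables and add the following.

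- **Both parts:** exposure-adjusted subject incidence per 100 subject-years, defined as subjects with a first event divided by time to first event or end of the treatment-emergent window. Report it for any TEAE, serious TEAEs, TEAEs leading to discontinuation and common preferred terms. State the end of that window explicitly, for subjects who roll over and for those who do not.
- **Part 1:** each dose-minus-placebo difference with a confidence interval. For the overview rows, add cumulative incidence at Week 40 with study exit as censoring or as a competing event, and say which. Censoring targets the risk had subjects stayed and needs exits independent of the AE. Treating exit as a competing event puts all arms on a common Week 40 cut-off, but without other censoring it returns the crude proportion to that date, so it does not remove the effect in step 1.
- **Part 2:** rates with confidence intervals for early-start low dose, early-start high dose and delayed start, with no placebo contrast.

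The cost is one SAP paragraph and a few table columns, from dates and exposure already collected. The rates assume a roughly constant hazard; in Part 1 the cumulative-incidence rows check this. Specifying the analysis before unblinding avoids a post hoc choice.

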- Hepatotoxicity: It is advised to monitor liver function tests regularly
- Pancreatitis: Caution is recommended in subjects with a history of pancreatitis
- Hemorrhage: Caution is indicated in subjects requiring medications that inhibit platelet function or anticoagulants
- Pregnancy: Women should be advised of the potential hazard to the fetus and to avoid becoming pregnant
- Compromised wound healing and gastrointestinal perforation

Nilotinib is approved for CML at doses up to 1200 mg daily (European Union) and up to 800 mg daily (United States of America), where it carries a black box warning for QT interval prolongation. Sudden cardiac death and electrolyte disturbances have been reported in patients taking nilotinib, and it can also cause myelosuppression. In non-clinical studies of nilotinib, potentially pro-arrhythmic effects as evidenced by inhibition of hERG current, prolongation of action potential duration, and induction of triangulation and beat-to-beat variability in the in-vitro assay systems were observed

n-vitro assay	y systems we	re observed			
-					
	 				
			 _	1 4: - : 4	

Ponatinib use is associated with hepatic impairment, neuropathy, ocular toxicity, and vascular occlusion (arterial and venous)

There has been one open-label trial of nilotinib of five subjects with Dementia with Lewy Bodies (a similar condition to PD with early cognitive impairment) and 7 subjects with mid to late-stage PD (all but one with cognitive impairment) SAEs in that study included myocardial infarction, hospitalization for urinary tract infection, and hospitalization for pneumonia. All other side effects were considered mild. Of note, most participants experienced increased psychotic symptoms and dyskinesias, which the authors noted suggested a symptomatic benefit of nilotinib (i.e., increased dopamine levels).

Regarding potential benefits, non-clinical evidence of efficacy in animal models of PD is described in section 2.2.3. There have been no studies in humans regarding the effectiveness of K0706 on Parkinson's disease.

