6.4.2 Use of Anti-clotting Agents

Serious bleeding events, including fatalities, have occurred in patients treated with K0706 in (section 2.2.5), as well as other Abl TKIs used for leukemia. Cerebral hemorrhage and gastrointestinal hemorrhage were the most commonly reported serious bleeding events in studies of other Abl tyrosine kinase inhibitors, with most hemorrhagic events occurring in patients with Grade 4 thrombocytopenia. Most likely, the cause of bleeding in these subjects was disease progression, but until further information is available, caution is indicated in patients requiring medications that inhibit platelet function or anticoagulants.

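### No visible safety table gives the number of subjects per arm with at least one bleed, although the protocol names serious bleeding as an unresolved risk of K0706

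*SAP*

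**What the plan says.** **The risk.** Protocol 6.4.2 (Use of Anti-clotting Agents) states: "Serious bleeding events, including fatalities, have occurred in patients treated with K0706". The study concerned is blacked out. The same section gives a view on cause and leaves it unresolved: "Most likely, the cause of bleeding in these subjects was disease progression, but until further information is available, caution is indicated". For the class it adds: "Cerebral hemorrhage and gastrointestinal hemorrhage were the most commonly reported serious bleeding events in studies of other Abl tyrosine kinase inhibitors", and says that most haemorrhagic events were in patients with Grade 4 thrombocytopenia. The class list in protocol 2.2.6 includes "Hemorrhage: Caution is indicated in subjects requiring medications that inhibit platelet function or anticoagulants", next to fluid retention, arrhythmia and heart failure.

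**The planned tables.** SAP 9.1 has:
- overview rows (any, treatment-related and serious TEAEs; those leading to discontinuation or death; by severity);
- tables by system organ class (SOC) and preferred term (PT), described as "The number and percentage of subjects reporting each TEAE and the count of number of events will be summarized by SOC and PT", with versions by maximum severity and by relationship;
- a table by PT alone, Part 1 tables by formulation, and listings.

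The counting rule is that "subjects with more than one TEAE within a particular SOC are counted only once for that SOC", with the same rule for a PT. Protocol 9.8.1 uses the same units, "The number and percentage of subjects reporting TEAEs will be tabulated by severity, system organ class, causality, and preferred term", and adds a summary by actual dose at onset. Neither section, as far as it can be read, defines a bleeding group, a standardised MedDRA query or adverse events of special interest.

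**The concern.** Whether K0706 raises the risk of bleeding is a question about subjects: how many in each arm had at least one bleed, and how many had a serious one. The planned tables split that count by anatomical site. The protocol itself names brain and gut, which sit in different SOCs, and nose, skin, urinary and post-injury bleeds would fall in others. Each of those SOC rows also contains events that are not bleeds.

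The question matters here because protocol 6.4.2 leaves causality open, with disease progression as the competing explanation. A placebo-controlled 40-week comparison in subjects with early Parkinson's disease can inform it. Safety is a secondary objective of Part 1 and the primary objective of Part 2. A modest excess scattered over many small rows is easy to overlook. A count assembled after unblinding is open to the criticism that its terms were picked with the results in view.

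**Working it through.** **1. Is a count of subjects with any bleed planned?** The visible safety sections (protocol 8.7 and 9.8; SAP 9.1 to 9.8) were read for one.
- The overview rows cover all TEAEs together and do not isolate bleeding.
- The SOC and PT tables, with their severity, relationship and formulation splits, show single organ classes or single terms.
- Platelet count, INR and aPTT appear only as laboratory summaries.
- SAP 9.6 points to composite endpoints in Section 13.5, whose visible text is blank. Nothing visible ties them to bleeding.
- SAP 8.2.1.3 does group adverse events by a PT list, for PD-symptom events in an efficacy analysis. The device is thus already in the SAP, but not for bleeding.

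**2. Can the count be recovered from the planned rows?** No, because subjects are de-duplicated only within a row. Take assumed PT counts of 3, 3, 2, 2, 2, 2 in one arm of 169.
- Smallest number of subjects consistent with these rows: the largest row, 3, so 3/169 = 1.8%.
- Largest number: the sum, 3+3+2+2+2+2 = 14, so 14/169 = 8.3%.

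The same table fits both.

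**3. How much could be hidden?** The documents state no bleeding rate and no power for safety, so there is no figure to reproduce and all rates below are assumptions. Arm size: 506 planned (protocol synopsis), randomised 1:1:1 (protocol 5.4.2), so 506/3 = 168.7, about 169. Method: sum the binomial probabilities of all pairs of counts for which the two-sided Fisher exact p is below 0.05.

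| Row | Assumed risk, placebo vs one dose | Expected subjects | Chance of p<0.05 |
|---|---|---|---|
| Any bleed | 5% vs 13% | 8.5 vs 22.0 | 68% |
| Any bleed | 4% vs 10% | 6.8 vs 16.9 | 51% |
| Any bleed | 2% vs 5% | 3.4 vs 8.5 | 21% |
| Any bleed | 3% vs 6% | 5.1 vs 10.1 | 18% |
| Any bleed | 5% vs 8% | 8.5 vs 13.5 | 14% |
| One PT, 5% vs 13% spread evenly over 8 | 0.625% vs 1.625% | 1.1 vs 2.7 | 2.3% |
| One PT, 4% vs 10% spread evenly over 6 | 0.67% vs 1.67% | 1.1 vs 2.8 | 2.4% |
| One PT carrying half of 5% vs 13% | 2.5% vs 6.5% | 4.2 vs 11.0 | 32% |

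A reader sees all the rows, not one. Treating rows as independent, the chance that at least one of the 8 even rows reaches p<0.05 is 1 − (1 − 0.0231)^8 = 17%, and for the 6-row case 1 − (1 − 0.024)^6 = 14%. Both remain well below the 68% and 51% of the grouped row.

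These figures compare how visible an excess is. They do not describe a planned test, since SAP 9.1 describes the AE summaries as descriptive.

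**The case against.** **Strength of the signal.** A reader might infer that K0706 is known to cause fatal bleeding, or has done so in Parkinson's subjects. The documents do not support that. The study is blacked out, the sentence goes on to other Abl inhibitors used for leukaemia, and the protocol considers disease progression the likeliest cause. The cerebral and gastrointestinal bleeds are reported for other drugs of the class. This stands: the risk is an open caution, and the case for counting it rests on its being open.

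**Nothing is lost.** A reader might also infer that bleeding will never be reported. That goes too far. All adverse events are listed by subject, serious and fatal TEAEs are tabulated by arm, the sponsor or CRO reviews safety data about monthly, and protocol 8.7 provides for a DSMB if concern arises. Some safety text cannot be seen: protocol 9.8.4 and part of 9.8.5, and SAP Sections 11 and 13.5. This also stands. The supportable statement is that no visible analysis gives the count. What is missing is the pre-specified summary, and a hand count made after unblinding does not replace it.

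**The size depends on the inputs.** With smaller excesses (5% vs 8%, 3% vs 6%, 2% vs 5%) the grouped row would also usually miss p<0.05, at 14% to 21%. An even split over terms is unfavourable to the PT rows, and one dominant term recovers much of the visibility. This stands, and so a range is given. It does not affect step 2, which needs no assumed bleeding rate: PT rows cannot be added to a subject count.

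**SOC and PT tabulation follows the protocol.** True. The point is that a better summary is cheaply available, not that the SAP departs from the protocol.

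**Conclusion.** The point holds as a gap in the visible plan. The protocol names serious bleeding as an unresolved risk, and neither SAP 9.1 nor protocol 9.8.1 visibly provides the number of subjects per arm with at least one bleed. That conclusion rests on the readable text and the counting rule, and SAP 9.1, where such a grouping would be expected, is nearly intact.

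The size is uncertain because the bleeding rates, the number of terms and the spread over terms are all assumed. At 169 per arm the grouped row has about a 14% to 68% chance of a two-sided Fisher p<0.05 over the rates tried. At 5% vs 13%, a single PT row has about 2% with an even spread over 8 terms and 32% if one term carries half the bleeds. Data collection and the efficacy analyses are unaffected. It is an inexpensive improvement to the safety reporting that should be made before unblinding.

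**What to change.** Add to SAP 9.1 a haemorrhage grouping, either a standardised MedDRA query or a PT list, fixed before the Part 1 treatment code is broken.
- **Both parts:** report by arm the number and percentage of subjects with at least one bleed and with at least one serious bleed.
- **Part 1:** add the risk difference of each dose from placebo with a 95% CI.
- **Part 2:** report by treatment group descriptively. All subjects then receive K0706, so there is no concurrent placebo comparison.
- **Anticoagulant or antiplatelet use:** any split should use baseline use only and be descriptive. Concomitant medication as defined in SAP 9.7 includes drugs started after the first dose, so splitting on it would condition on a post-randomisation variable that a bleed may itself change. The strata will be small.
- **Other class risks:** similar groupings for fluid retention, arrhythmia and heart failure are optional.

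The cost is a paragraph of SAP wording, one agreed term list and one more table. Adverse events are already MedDRA-coded and medications WHO-coded, so no new data are needed. The downside is a few more descriptive comparisons without multiplicity control, which the table should state. The change affects reporting only and touches no dose, schedule or clinical rule.
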